### **7.3. Subgroup analyses and effect modification**

We will assess for effect modification and exploratory subgroup analyses will be performed according to sex, age (categorized by < or  $\geq$  the median value in the study population), race, presence of pre-existing diabetes, body mass index (categorized by obese or non-obese), inpatient vs. outpatient status at the time of enrollment,  $\text{FiO}_2/\text{SpO}_2$  at the time of enrollment (categorized by < or  $\geq$  the median value in the study population), duration of symptoms prior to randomization (<7d vs.  $\geq$ 7 days) and fasting triglyceride levels (when available, categorized by < or  $\geq$  the standard median value).

## **8. PROTECTION OF HUMAN SUBJECTS**

### **8.1. Potential benefits of the proposed research, importance of the knowledge to be gained, and risk/benefit ratio**

Potential benefits: There are no known direct benefits to the subjects as a result of their participation in this study nor will this be implied when obtaining consent.

Potential risks: please refer to section 8.2

Importance of the knowledge to be gained: Our study will address a highly important clinical question that may impact the care of a large number of patients affected by the COVID-19 pandemic. This study will provide randomized trial evidence about the impact of a wide available, generic and inexpensive drug with a proven track record of safety for other indications (i.e., dyslipidemia). However, it is essential to rigorously and promptly study its potential clinical efficacy in a randomized controlled trial.

Risk/benefit ratio: given the importance of knowledge to be gained and the proven track record of safety of this medication, the risk/benefit ratio of our trial is favorable.

### **8.2. Risks to study subjects**

All subjects will be adults able to give informed consent. Subjects will be enrolled regardless of sex, race or ethnicity, aiming to assure adequate representation of women and ethnic minorities. Children will not be enrolled.

The risks to study subjects are related to the potential side effects of the study intervention. The dose used in this trial is the starting dose for primary hypercholesterolemia and mixed dyslipidemia and is utilized as a chronic therapy, for months or years. We propose to administer this dose for only 10 days.

With chronic therapy, adverse reactions > 2% and at least 1% greater than placebo include abnormal liver blood tests (increased AST and ALT) increased creatine kinase (CPK), and rhinitis. Rhabdomyolysis have been reported in patients taking fenofibrate, but is considered extremely

rare, with <20 cases reported worldwide for fibrate monotherapy. Moreover, the median duration of therapy prior to rhabdomyolysis was 17.5 days. In the Fenofibrate Intervention and Event Lowering in Diabetes (FIELD) trial, 9,795 were randomized to fenofibrate or placebo for 5 years. This provided >8 million patient-days of observation in the active arm alone. In this trial, only 3 patients allocated to fenofibrate had rhabdomyolysis, which in each case fully resolved; this incidence was not significantly different than that of the placebo arm (1 case of rhabdomyolysis). The risk of rhabdomyolysis may be increased during co-administration with a statin, in renal failure, or hypothyroidism. Accordingly, we will exclude all patients with advanced renal dysfunction and those with a history of hypothyroidism.

Regarding statins, although there is an increase in reports of rhabdomyolysis with statin-fibrate combined therapy, this risk appears to be much higher when statins are combined with gemfibrozil than fenofibrate. In a meta-analysis of 6 trials including 1,628 subjects taking fenofibrate in combination with statin therapy, no case of myopathy or rhabdomyolysis was reported. This included data from the LCP-AtorFen trial, in which atorvastatin (40 mg/d) was administered alone or with fenofibrate for 12 weeks, as well as some studies with simvastatin (20 mg/d).

The negligible risk of rhabdomyolysis with combination therapy has been repeatedly confirmed in subsequent studies. In the SAFARI trial (in which 411 patients received simvastatin 20 mg plus fenofibrate 160 mg/day) for 12 weeks, no cases of rhabdomyolysis were seen. In the FIELD trial of fenofibrate vs. placebo, no cases of rhabdomyolysis were seen among patients taking statin therapy. Finally, in the large ACCORD lipid trial, in which 5,518 patients with type 2 diabetes who were already being treated with simvastatin were assigned to receive either fenofibrate (160 mg) or placebo and followed for a mean of 4.7 years (representing ~12,995 patient-years of observation or ~4.7 M patient-days, in the fenofibrate+simvastatin arm alone), no increased risk of rhabdomyolysis was seen. In this trial, the administered simvastatin dose was up to 40 mg/d. The authors concluded that this is compatible with evidence that fenofibrate, in contrast to gemfibrozil, does not increase plasma concentrations of statins. Clinical data in large numbers of patients are also available for pravastatin and rosuvastatin. The lack of significant increase in concentrations of statins induced by fenofibrate has been shown specifically for simvastatin, pravastatin atorvastatin and rosuvastatin. For pravastatin, fenofibrate may slightly increase the AUC for its metabolite 3-alpha-hydroxy-iso-pravastatin, which is not considered clinically concerning given its much lower potency and lack of toxicity compared to the parent drug; moreover, subsequent careful studies with dosing of up to 15 days showed no increased AUC for pravastatin or its metabolite 3alpha-hydroxy-iso-pravastatin. The lack of clinically significant interactions with these statins is a clear difference with gemfibrozil, which unlike fenofibrate, does increase the AUC of atorvastatin, simvastatin, and multiple other statins. There is, however, an increased AUC for pravastatin and fluvastatin and there is much less data for newer statins. Cases of myopathy, including rhabdomyolysis, have been reported with fenofibrates co-administered with colchicine. A Pubmed search of "colchicine AND fenofibrate" (search performed on August 10th, 2020) returned 11 articles, of which only one was a report of a case of myopathy in patient receiving these drugs, which actually worsened upon discontinuation of fenofibrate and was ultimately proven to be due to inflammatory/autoimmune myopathy (based on biopsy data) and associated with multisystemic autoimmune disease. In contrast, we found a reported case with co-administration of colchicine and gemfibrozil and one with bezafibrate, both of which resolved upon discontinuation of the medications. Therefore, this does not appear to be a significant problem with fenofibrate and in fact, fenofibrate has been suggested as a treatment for gout, a patient population in which colchicine is very common.

Given that we will only administer 10 days of therapy, we consider the risk of rhabdomyolysis, even in patients taking statins or colchicine, to be negligible. Nevertheless, as a precaution, we will exclude patients who are taking statins other than simvastatin and atorvastatin; similarly, we will exclude patients who are taking simvastatin or atorvastatin at doses >40 mg/d,

since doses >40 mg/d of these 2 drugs in combination with fenofibrate have not been specifically studied. Finally, we will ask site investigators to communicate any occurrence of rhabdomyolysis to the Principal Investigator, who in turn will immediately communicate them to the DSMB for a formal assessment (with unblinding of the DSMB if required). We will inquire about potential manifestations of rhabdomyolysis (particularly hemoglobinuria) in all data collection forms and the study medication will be discontinued immediately upon suspected or confirmed rhabdomyolysis.

Fenofibrate can increase serum transaminases and/or serum creatinine and periodic monitoring is recommended during chronic therapy. However, we will only utilize it for 10 days in this trial and will exclude patients with active liver disease or advanced renal disease. Therefore, the need for periodic monitoring does not apply for such as short treatment. Moreover, the mild increase in serum creatinine is not thought to be due to impaired true glomerular function, as measured by inulin clearance, the gold standard measure of renal function. This creatinine rise does not increase the risk of adverse renal outcomes or cardiovascular events, and is fully reversible upon discontinuation.

Fenofibrate increases cholesterol excretion into the bile, leading to risk of cholelithiasis. This is not anticipated to be a problem with 10 days of therapy, and our trial will exclude patients with a history of gallbladder disease. As recommended by the approved prescribing information, we will also exclude nursing mothers, and patients with known hypersensitivity to fenofibrate or fenofibric acid.

Fenofibrate can also rarely cause allergic reactions and mild to moderate changes in blood cell counts. Pancreatitis has been observed (in post-marketing case reports) in people taking fenofibrate for dyslipidemia, but is an extremely rare occurrence. Of note, the overwhelming majority of these reports involved patients who had other, more strongly associated risk factors for acute pancreatitis and it is unclear whether and to what degree was fenofibrate causally involved. Moreover, the incidence of pancreatitis has been estimated to be very low (0.13 per 100 patient years on monotherapy and 0.16 per 100 patient years in combination with a statin) and such a complication is extremely unlikely with 10 days of therapy.

Drugs that exhibit significant interactions with fenofibrate include coumarin anticoagulants, immunosuppressants and glimepiride. We will exclude patients taking these medications.

### **8.3. Adequacy of Protection Against Risks**

#### **8.3.1. Recruitment and Informed Consent:**

Electronic informed consent will be obtained from the subjects or their authorized representatives prior to entry into the research study. Potential subjects will receive the IRB approved informed consent form in person or electronically to minimize risk of exposure to SARS-CoV-2. The principal investigator or sub-investigators will conduct the informed consent process in person, or via phone or video conferencing, which maximizes the efficiency of workflow and minimizes exposure of the research staff to SARS-CoV-2. When a physical ICF is utilized, for safety reasons, the copy of the physical ICF will not be retrieved from the patient's room or hospital area, and only a photograph of the signed page of the informed consent form will be kept in the electronic regulatory files.

The study intervention and potential associated risks will be explained to study subjects and they will have adequate time to ask questions. No study interventions will be initiated until the study team receives either the signed informed consent form or attestation documenting the subjects' agreement to participate.

**8.3.2 Measures to minimize the risk of breach in confidentiality:** All records will be treated with strict confidentiality according to guidelines and regulations related to Sensitive Patient Health Information in respective countries. Our eCRFs will be contained in secure servers at the University of Pennsylvania. A secure database of patient information will be maintained. All

documents for this trial will be electronic, but any unanticipated paper files that contain protected health information will be saved under lock in a secure area.

## **9. REGULATORY STANDARDS**

The study will be submitted to the site's IRB/EC for approval. During the study, any amendment or modification to the protocol will be sent to the IRB/EC. Protocol deviations will be handled according to Institutional guidelines. In each country, the National Principal Investigator will lead and hold responsibility for federal regulatory processes. All site PIs will be responsible for obtaining IRB/research ethics committee approval from their respective boards and to comply with their national and institutional regulations.

## **10. ADAPTIVE DESIGN**

The trial, including any interim safety and efficacy analyses, will be monitored by an independent DSMB. The DSMB will have the capacity to recommend termination of enrollment based on new available evidence of interim data analyses, as detailed in our DSMB charter. If the trial is terminated prematurely for any reason, follow-up will continue for all randomized participants. An increase in the sample size will be considered depending on feasibility and pace of enrollment, to enhance the power of the study for secondary endpoints. New trial arms can be added as evidence emerges that other candidate therapeutics should be evaluated. Any modification to the protocol will require approval by applicable institutional review boards/Ethics committees at enrollment sites, as well as applicable regulatory agencies in each enrollment country.

## APPENDIX 1. DYSPNEA BORG SCALE AND COVID-19 SYMPTOM SCALE

“This is a scale that asks you to rate the difficulty of your breathing. It starts at number 0 where your breathing is causing you no difficulty at all and progresses through to number 10 where your breathing difficulty is maximal. How much difficulty is your breathing causing you with your usual activities today?”

### COVID-19 Symptom scale

Rate each of the following symptoms from 0-10 (scale similar to the one above)

- Fever or Chills
- Cough
- Muscle or body aches
- Sore throat
- Loss of smell or taste
- Headache
- Diarrhea
- Fatigue
- Nausea or vomiting
- Chest pain or discomfort

All scores for individual symptoms (including dyspnea, as per the dyspnea Borg scale) are added to compute the final score.

## APPENDIX 2. SCHEDULE OF EVENTS

	At Enrollment	Daily During admission	~5 days post-enrollment	~10 days post-enrollment	~15 days post-enrollment	~30 days post-enrollment
All participants						
Screening for Inclusion eCRF	X					
Informed Consent	X					
Randomization	X					
Baseline Medical Information eCRF	X					
Inpatients		X				
Daily Inpatient Information eCRF		X				
Follow-up call eCRF						X
Outpatients						
Follow-up call eCRF			X	X	X	X

Adverse Event Forms, deviation event logs and withdrawal forms will be filled at any time during the study, as needed.

## APPENDIX 3. COUNTRY-SPECIFIC FENOFIBRATE PREPARATION, INFORMED CONSENT MECHANISM AND REGULATORY ISSUES

**NOTE:** This appendix varies in each country according to various factors in each country, including the fenofibrate preparation utilized and applicable regulatory requirements in a given country. Only information about the preparation that applies to each country will be submitted for review and regulatory approval in the respective country.

### UNITED STATES:

#### *Fenofibrate preparation and dosing*

In the US, the drug and placebo will be prepared (encapsulated) by the Penn Investigational Drug Pharmacy. It will be shipped to IDS services in other enrollment sites. Administration will be double-blinded (Investigators and patient).

We will utilize Tricor tablets. The dose will be 145 mg/day with appropriate dose correction for patients with chronic kidney disease (CKD). The daily dose of Tricor for patients with CKD stage 2 will be 96 mg/d and the dose for CKD stage 3 will be 48 mg/d. In all cases, the intended duration of randomized treatment will be for 10 days.

The medication will be administered by mouth regardless of meals; in patients who are intubated, we will administer the crushed tablet (or placebo) via nasogastric tube. The latter procedure requires opening the capsule and therefore unblinds the administering nurse, which is acceptable, since in that setting (once the patient is intubated), subjective endpoints do not influence the study primary (only time to death and days of mechanical ventilation do, in tiers 1 and 2). The same is true for all secondary outcomes. Moreover, the patient and investigator will remain blinded. We have considered the alternative of preparing a blinded solution of active medication vs. placebo by IDS to be sent to the floor for administration via NG tube; however, we lack reliable data regarding the stability of the medication in solution at ambient temperature for various periods of time. Therefore, we have opted against this option.

#### *Baseline evaluation*

In addition to documentation of SARS-CoV infection, baseline laboratory test should include at a minimum, a creatinine level for assessment of eGFR (to determine the appropriate medication dose). These are done routinely as part of clinical care at Penn (Emergency room visits or inpatient assessments). We will also consider outpatients who reach out to us as a result of advertisements. If these participants have already had these tests elsewhere (i.e., other medical facilities), we will accept documentation of such tests. Otherwise, we will invite outpatient patients to the Center for Human Phenomics Sciences to undergo any necessary tests as per protocol.

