**Exclusion Criteria:**

- (1) Known pregnancy or breastfeeding.
- (2) Estimated glomerular filtration rate (eGFR) <30 mL/min/1.73m^2 or undergoing dialysis (CKD stages 4-5).
- (3) History of active liver disease, cholelithiasis, uncontrolled hypothyroidism, or rhabdomyolysis (suspected or confirmed). Patients with a history of hypothyroidism receiving a stable dose of thyroid replacement therapy for at least 6 weeks, with a documented normal TSH (primary hypothyroidism) or free thyroxine (secondary or tertiary hypothyroidism) level at least 6 weeks after the last dose change will be considered eligible for enrollment.
- (4) Known hypersensitivity to fenofibrate or fenofibric acid.
- (5) Ongoing treatment with fenofibrate, clofibrate, warfarin and other coumarin anticoagulants, glimepiride, cyclosporine, tacrolimus.
- (6) Use of statins other than simvastatin, pravastatin or atorvastatin ≤40 mg/d or rosuvastatin ≤20 mg/d.
- (7) Prisoners/incarcerated individuals
- (8) Inability to read, write or no access to a smart phone, computer or tablet device.
- (9) Intubated patients.

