## **2.7. Participant withdrawal / Early termination**

Participants may voluntarily withdraw from the study at any time and for any reason. The reason for study discontinuation will be recorded on the source documents and in all such participants, we will document: (1) vital signs (inpatients only); (2) compliance with the treatment; (3) adverse effects. (4) specific reason for withdrawal if possible; (5) functional status and symptoms (including the dyspnea Borg scale).

The study medication will be discontinued if any of the following occur at any time: (1) acute kidney injury with eGFR<30 ml/m^2/min; (2) Suspected or confirmed rhabdomyolysis; (3) Red or brown urine, which may indicate myoglobinuria, unless considered by the investigator to be clearly not due to rhabdomyolysis (for instance, in the presence of normal circulating creatine kinase); (4) Liver failure or increased AST or ALT to >3 times the upper limit of normal. In cases in which the medication is discontinued, data collection will continue normally as per the usual study protocol.

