#### Classification of Adverse Events for Causal Relationship to the Study Intervention

---

Not related or unlikely related	There is not a reasonable causal relationship to the investigational product and the adverse event, or there is a low likelihood that a causal relationship exists.
Probably or definitely related	There is reasonable or definite evidence to suggest a causal relationship between the drug and adverse event.

---

The events will be classified as serious or non-serious adverse events:

*Serious Adverse Events (SAE)* are adverse events, in which the investigator or sponsor believe that any of the following outcomes occur:

- Death
- Life-threatening AE: Places the participant at immediate risk of death at the time of the event as it occurred. It does not include an AE that, had it occurred in a more severe form, might have caused death.
- Persistent or significant incapacity or substantial disruption of the ability to conduct normal life functions.
- Inpatient hospitalization or prolongation of hospitalization.
- Important medical events that may not result in death, be life threatening, or require hospitalization may be considered a serious adverse event when, based upon appropriate medical judgment, they may jeopardize the participant and may require medical or surgical intervention to prevent one of the outcomes listed in this definition above.

Expectedness: Expected AEs will be those that are reported to be associated with COVID-19.

The following AEs are expected, disease-related events in patients with COVID-19

1. Arrhythmias, including ventricular arrhythmias and atrial fibrillation.

2. Acute coronary syndromes with or without coronary stenoses on coronary angiography
3. Myocarditis or worsening cardiac function.
4. Shortness of breath, pneumonia, acute respiratory distress syndrome and respiratory failure.
5. Fever, malaise and myalgia.
6. Worsening cognitive function.
7. Limb ischemia, coagulopathy, thrombosis, embolus.
8. Hypotension or hypertension.
9. Diarrhea, nausea, or vomiting.
10. Anosmia (loss of sense of smell).
11. Leukopenia or leukocytosis, thrombocytopenia.
12. Worsening renal function (resulting in various electrolyte abnormalities).
13. Worsening liver function.
14. Death.

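### Study drug stops when AST or ALT exceeds three times the upper limit of normal, but no entry limit and no required US baseline test keeps out a participant already above it

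*Protocol*

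**What the plan says.** **Stopping rules.** Protocol Section 2.7 lists the events that end study drug. The first is renal: "The study medication will be discontinued if any of the following occur at any time: (1) acute kidney injury with eGFR<30". The fourth is hepatic: "Liver failure or increased AST or ALT to >3 times the upper limit of normal". Follow-up and data collection continue after a stop.

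**Entry criteria.** In Section 2.3 the renal exclusion carries a number: "Estimated glomerular filtration rate (eGFR) <30" (or dialysis). The liver exclusion does not: "History of active liver disease, cholelithiasis, uncontrolled hypothyroidism, or rhabdomyolysis (suspected or confirmed".

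**Baseline tests.** Appendix 3 for the United States requires documentation of infection and says that the "baseline laboratory test should include at a minimum, a creatinine level for assessment of eGFR (to determine the appropriate medication dose". AST and ALT are not named. It accepts results obtained elsewhere, and it offers outpatients who respond to advertisements whatever further tests the protocol requires. The schedule of events in Appendix 2 names forms at enrolment but no laboratory panel.

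**Monitoring.** Section 8.2 declines periodic testing of transaminases and creatinine because treatment lasts ten days and the trial "will exclude patients with active liver disease or advanced renal disease".

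**Known liver effects.** Section 8.2 says of chronic therapy that "adverse reactions > 2% and at least 1% greater than placebo include abnormal liver blood tests (increased AST and ALT". Section 4.3 lists "Worsening liver function" among the events expected from COVID-19 itself.

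**The concern.** The protocol judges that a transaminase above three times the upper limit of normal (ULN) is a reason to take a participant off the drug. Nothing in the written criteria stops a person at that level from being started on it. Both the disease and the drug can raise these enzymes, by the protocol's own account, so the situation is foreseeable.

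Two things are at stake. The first is participant safety: someone past the stop limit can be dosed, and with no scheduled test the elevation may never be found. The second is how liver findings are read. If a high value turns up in usual care during the ten days, a site with no baseline value cannot say whether it arose on treatment.

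**Working it through.** No published figure has to be reproduced. The check sets the provisions side by side.

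| Provision | Kidney | Liver |
|---|---|---|
| Stop rule (Protocol 2.7) | Acute kidney injury with eGFR below 30 | Liver failure, or AST or ALT above 3 × ULN |
| Entry limit (Protocol 2.3) | eGFR below 30, or dialysis | History of active liver disease; no enzyme level |
| US baseline minimum (Appendix 3) | Creatinine | None named |
| Laboratory panel in schedule (Appendix 2) | None named | None named |
| On-treatment testing (Protocol 8.2) | None planned | None planned |

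1. *Kidney.* The entry and stop limits are the same number, and a required test shows on which side of it a US participant lies.
2. *Liver.* The stop has a number; the entry criterion has none, and no required US test would supply a value. No other place in the Protocol or SAP gives an AST or ALT entry limit or requires a baseline liver test.
3. *A patient who passes.* Take an adult with confirmed COVID-19, no liver history, eGFR above 30, and AST at four times ULN because of the infection. No written criterion excludes this person.
4. *Two readings of the stop rule.* If it covers any value above the limit, this participant qualifies for a stop from the first day, as soon as somebody measures AST. If it covers only a rise during the study, applying it needs a baseline value, which is not required. Both readings leave a gap.
5. *Would it be noticed?* Only if usual care happens to test. This is least assured for US outpatients recruited by advertisement, who need only the tests that the protocol names.
6. *The reason for not monitoring.* Section 8.2 rests partly on the exclusion of active liver disease. For the liver, no required test supports that exclusion. The choice not to monitor a ten-day course is not itself disputed here.

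**How many?** The share p of otherwise eligible patients above 3 × ULN at entry is not in the documents. For scale only, assume p = 2%, 5% or 10%:

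- Participants past the stop limit among 700 randomised, 700 × p: 14, 35, 70.
- Otherwise eligible patients needed to randomise 700 if all such patients were excluded, 700 / (1 − p): about 714, 737, 778.

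**The case against.** The strongest reply has four parts.

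- *The contrast with the kidney has a stated reason.* Creatinine is required because dose depends on renal function, not as the partner of a stop rule. This stands. It explains why creatinine is on the list. It does not supply a liver entry limit.
- *The stop rule reads naturally as an on-study event, and a site without a baseline value can stop on any high result, which is the safe direction.* This stands once a result exists. It does nothing for an elevation that nobody measures.
- *Liver protection at entry exists.* An investigator who sees a marked elevation can treat it as active liver disease, and many inpatients will have AST and ALT from routine care. The protocol also allows more tests than its minimum. This is fair and narrows the gap, but it depends on a value being to hand and on judgment, where the renal criterion depends on neither.
- *A universal mandatory test is not free.* Appendix 3 accepts outside creatinine results, so an outpatient without AST or ALT could need a new blood draw in a trial that tries to limit staff exposure. This stands, and it shapes the fix.

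A reader might also infer that the primary analysis loses power, because participants stopped at once still count as randomised. The documents do not support that. It would need nearly all of them to be measured soon after randomisation and stopped with no benefit, yet no such measurement is required. An unmeasured participant has no transaminase result to trigger a stop.

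**Conclusion.** The mismatch is real and rests on the text alone: a participant can be randomised and dosed while already above the protocol's liver stopping level. It is worth correcting because the remedy is cheap and the benefit falls on participant safety and on the interpretation of liver findings. Its frequency is unknown, and the counts above are illustrations under assumed shares.

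Three limits apply. The missing entry limit is in the main protocol and so holds in every country. The missing baseline test is shown for the United States only, since other countries' appendices are not available. The content of the baseline case report form is not shown either.

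A reader might go on to infer a specific distortion of the comparison of hepatic adverse events between arms. No figure for that is warranted. The rates in Section 8.2 concern any abnormal liver test under chronic therapy, which is a different threshold and duration from 3 × ULN within ten days. The SAP's Safety Analysis plans frequencies and exact binomial intervals, not a ratio of arms. Nor do the documents show that liver enzymes go unmeasured in practice; they show only that measurement is not required.

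**What to change.** 1. **Protocol Section 2.3, exclusion (3).** Add: an AST or ALT more than three times ULN on any result available from the current illness.
2. **Appendix 3 (United States), Baseline evaluation.** Add AST and ALT wherever blood is drawn for the baseline creatinine. Where outside documentation is accepted, record any AST and ALT that it contains.
3. **SAP, Safety Analysis.** Where a baseline value exists, count a transaminase above 3 × ULN as arising on treatment only if the baseline value was at or below that limit.

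No on-treatment test is added.

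**Cost.** Two assays on a sample already being drawn. Some patients with COVID-related elevation become ineligible. The screening figures above (about 714 to 778 for 700 randomised, under the assumed shares) are the most this would require at those shares, because only patients with a result can be excluded. Patients with an outside creatinine and no transaminase result would still enter unmeasured. Closing that remainder needs a mandatory test, which could mean a new draw for those outpatients. The burden at sites outside the US cannot be judged from the documents.
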